14.2 Secondary Analyses

All secondary analyses will be based on the ITT population. Raw scores will be presented in patient listings.

The secondary efficacy variables will be summarized at Days 4, 8, and 21 for absence of anterior chamber cells and at Days 8, 15 and 21 for absence of ocular pain using counts and percentages as described for the primary efficacy summaries. Additionally, anterior chamber cell grade and ocular pain score at each visit and change from baseline will be summarized using continuous and discrete summary statistics.

Anterior chamber flare is graded on a 5-unit scale where 0 = None, 1+ = Faint, 2+ = Moderate (iris and lens details clear), 3+ = Marked (iris and lens details hazy) and 4+ = Intense (fibrin or plastic aqueous).

Absence of anterior chamber flare and anterior chamber flare grade and the sum of anterior chamber 13/FEB/2014

Confidential

Page 16 of 21

Statistical Analysis Plan Protocol RTA 408-C-1307

Version 1.0

cell and flare grade, including absence of both anterior chamber cell and flare, will be summarized at each visit in the same fashion as described for the primary analyses of anterior chamber cells and ocular pain.

The ITT population will be used for the secondary analyses. The secondary analysis variables will be presented in patient listings.

15. Safety

All safety analyses will be conducted using the Safety Population. All safety data will be listed by patient and visit, as applicable.

15.1 Adverse Events

An Adverse Event (AE) is defined as any untoward medical occurrence associated with the use of a drug in humans, whether or not the event is considered drug-related. An AE can therefore be any unfavorable and unintended sign (e.g., an abnormal laboratory finding), symptom, or disease occurring after the first dose of study drug, without any judgment about causality. Any pre-existing medical condition that worsens after first administration of the study drug will also be considered a new AE. The AE reporting period ends upon study exit. Study drug includes the investigational drug under evaluation and placebo given during any stage of the study. All AEs will be coded using the MedDRA dictionary, version 16.1.

Treatment-emergent adverse events (TEAEs) are defined as any event that occurs or worsens on or after the day that randomized study treatment is initiated. Adverse events recorded in the eCRF which began prior to treatment will not be included in the summary tables but will be included in the AE data listings.

An overall summary will be presented that includes the number of TEAEs and the number and percentage of patients who experienced at least one TEAE, by treatment group and overall. This summary will also include breakdowns of TEAEs further categorized as ocular (study eye and fellow eye separately) or non-ocular, serious TEAEs (SAEs), TEAEs by maximum severity, TEAEs by maximum relationship, and AEs leading to patient withdrawal.

Severity of an AE is defined as a qualitative assessment of the degree of intensity of an AE as determined by the Investigator or reported to him/her by the patient. The assessment of severity is made irrespective of relationship to study drug or seriousness of the event and should be evaluated according to the following scale:

- Mild: Event is noticeable to the patient, but is easily tolerated and does not interfere with the
 patient's daily activities.
- Moderate: Event is bothersome, possibly requiring additional therapy, and may interfere with the
 patient's daily activities.

Statistical Analysis Plan Protocol RTA 408-C-1307

c-1307 1.0

Version

 Severe: Event is intolerable, necessitates additional therapy or alteration of therapy, and interferes with the patient's daily activities.

The relationship of each AE to the study drug should be determined by the Investigator using these explanations:

- Suspected: A reasonable possibility exists that the study drug caused the AE.
- Not Suspected: A reasonable possibility does not exist that the study drug caused the AE.

Additional summaries of TEAEs will be provided showing the number and percentage of patients who experienced at least one TEAE. These summaries will be presented by system organ class (SOC) and preferred term (PT). Non-ocular TEAEs will be summarized using discrete summary statistics and presented by treatment group at the patient and event level by System Organ Class (SOC) and Preferred Term (PT). Ocular TEAEs will be similarly summarized at the patient level for study and fellow eyes separately. If a patient reports the same PT multiple times within the same SOC, that PT will only be reported once within that SOC. As with the PT, if a patient reports multiple conditions within the same SOC, that SOC will only be reported once. The occurrence of non-ocular and ocular TEAEs will also be tabulated by SOC and PT for the following: maximal severity and suspected relationship to study drug.

Separate listings will be provided for all AEs, AEs leading to treatment discontinuation, and SAEs.

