Summaries for continuous variables will include the sample size (n), mean, standard deviation, median, minimum, and maximum. Summaries for discrete variables will include frequencies and percentages. Differences between treatment groups will be calculated as Test – Placebo and change from baseline will be calculated as follow-up visit – baseline. The baseline visit will be defined as the last non-missing measure prior to initiation of investigational treatment. All efficacy analyses will use a one-sided alpha=0.10 test unless otherwise stated.
The secondary efficacy variables, study eyes with absence of anterior chamber cells (Visits 3, 4 or 6), study eyes with absence of pain (Visits 4, 5 or 6) and study eyes with absence of flare (Visits 3, 4, 5 or 6) will be summarized similarly to the primary efficacy summaries. Additionally, anterior chamber cells and flare as well as pain at each visit and change from

	baseline will be summarized using continuous and discrete summary statistics.
	The sum of anterior chamber cells and flare grade will be summarized similarly to anterior chamber cells and flare separately.
	Safety Analysis:
	The primary safety analysis will summarize ocular treatment emergent AEs (TEAEs) in the study eye for all treated patients using discrete summaries at the patient and event level by system organ class and preferred term for each treatment group. A TEAE will be defined as any AE that occurs after the treatment is initiated. An additional analysis will examine ocular AEs for the non-study eye. Non- ocular TEAEs will be summarized using discrete summaries at the patient and event level by system organ class and preferred term for each treatment group. Treatment related ocular and non-ocular TEAEs will be summarized similarly. Ocular and non-ocular TEAEs will also be summarized by severity.
	The IOP data will be summarized at each visit using both continuous summaries (including change from baseline) and discrete summaries (including the proportion of patients with change in IOP from baseline ≥ 10 mm Hg and the proportion of patients with an IOP ≥ 30 mm Hg that occurs at any time following initiation of study treatment) as well as shift tables.
	Slit lamp biomicroscopy and dilated indirect ophthalmoscopic examination measures will be summarized at each visit using discrete summary statistics.

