10.12 Safety Analyses

The primary safety analysis will summarize ocular treatment-emergent AEs (TEAEs) in the study eye for all treated patients using discrete summaries at the patient- and event-level by system organ class and preferred term for each treatment group. A TEAE will be defined as occurring on or after the day that treatment is initiated. An additional analysis will investigate ocular AEs for the non-study eye. Non-ocular TEAEs will be summarized using discrete summaries at the patient- and event-level by system organ class and preferred term for each treatment group. Treatment-related ocular and non-ocular TEAEs will be summarized similarly. Ocular and non-ocular TEAEs will also be summarized by severity.

The IOP data will be summarized at each visit using both continuous summaries (including change from baseline) and discrete summaries (including the proportion of patients with change in IOP from baseline ≥ 10 mm Hg and the proportion of patients with an IOP ≥ 30 mm Hg that occurs at any time following instillation of study treatment) as well as shift tables.

Slit lamp biomicroscopy and dilated indirect ophthalmoscopic examination measures will be summarized at each visit using discrete summary statistics.

Visual acuity data will be summarized at each visit, using discrete summaries, including change from baseline in the number of lines and the proportion of patients with change from previous visit of ≥ 2 lines.

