15.5 Intraocular Pressure (IOP)

Intraocular pressure (IOP) will be assessed in both eyes by Goldman applanation tonometry at each visit. Results will be taken from a single measurement and will be recorded in mmHg.

The IOP values and changes from baseline for each eye (study eye and non-study eye) will be summarized using descriptive statistics (number of observations, mean, SD, median, minimum, and maximum values) by visit and eye for each treatment group and for all patients combined. In addition, the proportion of patients with an increase in IOP ≥10 mm Hg from baseline and the proportion of patients with an IOP ≥30 mm Hg at the visit will be presented using frequency counts and percentages. A patient listing of IOP will also be produced.

16. Interim Analyses

There are no planned interim analyses.

17. Changes from Protocol-Stated Analyses

The imputation methodology for the Per Protocol population, described in Section 9.2 of this SAP, differs from that described in the Protocol. The SAP accurately reflects how data will be handled for patients who are discontinued from study treatment due to lack of efficacy.

18. Reporting Conventions

Reporting conventions will adhere when possible to the International Conference on Harmonization (ICH) Guidance E3, "Structure and Content of Clinical Study Reports". All tables and listings will be presented in landscape format. All SAS output for tables and listings will be distributed in PDF files.

19. Revisions History

Documentation of revision to the SAP will commence after approval of the Final version 1.0.

Statistical Analysis Plan Protocol RTA 408-C-1307

Version 307 1.0

20. Tables

Table		Population
Number	Title	Intent-to-Treat
14.1.1	Summary of Analysis Populations, All Patients	Intent-to-Treat
14.2.2.1	Patient Disposition	
14.1.2.2	Patient Disposition	Per Protocol
14.1.3	Significant Protocol Deviations	Safety
14.1.4.1	Demographic Characteristics	Safety
14.1.4.2	Demographic Characteristics	Intent-to-Treat
14.1.4.3	Demographic Characteristics	Per Protocol
14.1.5.1	Non-Ocular Medical History	Intent-to-Treat
14.1.5.2	Ocular Medical History	Intent-to-Treat
14.1.6.1	Non-Ocular Prior and Concomitant Medication Use, Classified by WHO ATC Drug Classification	Intent-to-Treat
14.1.6.2	Ocular Prior and Concomitant Medication Use, Classified by WHO ATC Drug Classification	Intent-to-Treat

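### SAP 15.1 omits event counts by SOC and PT for study-eye ocular TEAEs, although the protocol makes them part of its primary safety analysis, and SAP section 17 does not declare the change

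*SAP*

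**What the plan says.** Protocol 10.12 names its main safety analysis: "The primary safety analysis will summarize ocular treatment-emergent AEs (TEAEs) in the study eye for all treated patients", to be done "using discrete summaries at the patient- and event-level by system organ class and preferred term for each treatment group". The synopsis sets the same requirement: "using discrete summaries at the patient and event level by system organ class and preferred term for each treatment group". Protocol 10.12 asks for the same two levels for non-ocular TEAEs and says that treatment-related TEAEs are to be handled in the same way. For the non-study eye it mentions only a further analysis and gives no counting level.

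SAP 15.1 treats the two kinds of event differently. For non-ocular events: "Non-ocular TEAEs will be summarized using discrete summary statistics and presented by treatment group at the patient and event level". For ocular events: "Ocular TEAEs will be similarly summarized at the patient level for study and fellow eyes separately". A counting rule follows both sentences: "If a patient reports the same PT multiple times within the same SOC, that PT will only be reported once within that SOC".

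SAP section 17, on changes from the protocol-stated analyses, names one departure: "The imputation methodology for the Per Protocol population, described in Section 9.2 of this SAP, differs from that described in the Protocol". It says nothing about adverse event summaries.

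Two other outputs in SAP 15.1 bear on the point. An overall TEAE summary gives the number of events as well as the number of patients by arm, with ocular study-eye, ocular fellow-eye and non-ocular breakdowns. All adverse events are also listed individually.

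**The concern.** The protocol's primary safety analysis has a patient-level half and an event-level half. As written, the SAP delivers the first for the treated eye but not the second, and a reader of SAP section 17 would not learn that anything had changed.

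The split also runs against the trial's own emphasis. The synopsis describes this as the first clinical study of the ophthalmic suspension. The nonclinical ocular finding it reports is conjunctival irritation in one rabbit study under frequent dosing, described as reversible and easy to monitor. The introduction regards meaningful systemic exposure from topical use as highly unlikely. Yet counts of events by term are kept for non-ocular events and dropped for the eye that receives the drops. Patients instill study drug twice daily for 14 days, or 2 × 14 = 28 doses, so an event linked to instillation has the opportunity to recur. With two concentrations under study, two arms could show similar patient incidence for a term and still differ in the number of events for that term.

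**Working it through.** The plan states no figure to reproduce. The check is a comparison of text, followed by the arithmetic of the counting rule.

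**Required and planned summaries by SOC and PT**

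| TEAE group | Protocol 10.12 and synopsis | SAP 15.1 |
|---|---|---|
| Study-eye ocular | patient and event level | patient level |
| Treatment-related, study-eye ocular | same as above | by relationship; no event level stated for ocular |
| Non-ocular | patient and event level | patient and event level |
| Non-study-eye ocular | no level stated | patient level |
| By severity | no level stated | maximal severity, so one value per patient |

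Only the first two rows conflict.

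**Can the SAP wording be read as consistent with the protocol?**

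1. The ocular sentence says that the summary is done in a similar way to the non-ocular one, which might be thought to carry the event level over. It does not, because the same sentence then names the patient level alone. The sentence just before it names both levels, so the contrast is explicit.
2. The SAP's list of tables gives TEAE tables by SOC, and one by relationship to study drug, without stating a counting level. It does not restore the event level.
3. SAP 12.1 uses the same split for medical history: non-ocular at both levels, ocular at patient level. That suggests carried-over wording rather than a deliberate choice. This is an inference, and the mismatch stands on either explanation.

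**What the counting rule does**

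Suppose m of the N patients in an arm each have k study-eye episodes recorded under one PT.

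- SAP ocular SOC/PT table: m patients, 100·m/N percent, whatever k is.
- Protocol event-level summary: m·k events in addition.
- Events not shown by term: m·k − m = m(k − 1).

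The planned arm size is N = 35 (protocol section 4). The values of m and k below are assumptions chosen only to show the mechanism. Neither document gives an expected incidence or repeat rate. With m = 10, the patient percentage is 10/35 = 28.6% throughout.

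| k (assumed) | Printed in SAP table | Events (m·k) | Not shown by term |
|---|---|---|---|
| 1 | 10 (28.6%) | 10 | 0 |
| 2 | 10 (28.6%) | 20 | 10 |
| 6 | 10 (28.6%) | 60 | 50 |

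All m·k events still enter the all-terms study-eye total in the overall summary and the listings. What is lost is the tabulation by term and arm.

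**The case against.** **Repeat events are not lost from the SAP.** A reader might infer that repeated ocular reactions count as one throughout the analysis. The documents do not support that. The overall TEAE summary carries event totals by arm with a study-eye breakdown, so a general excess of repeat events would show there. This stands, and it confines the point to the SOC/PT tables. The total cannot show which term recurs, however.

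**Every event can be retrieved.** A reader might also infer that the event counts cannot be found by term at all. With about 105 patients and a full adverse event listing, they could be counted by hand. That too stands. A listing is still not the per-arm summary by SOC and PT that the protocol requires.

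**The once-per-patient rule is ordinary.** It follows the non-ocular sentence as well and is standard for patient-level counts. The defect is the missing event count, not the rule.

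**Recurrence may matter little.** Neither document calls recurrence the key safety signal. Adverse events are recorded with onset and end dates, so continuous irritation could be a single record and event counts might add nothing. It is therefore right to claim no size.

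**Tolerability is covered elsewhere.** SAP 15.2 plans slit-lamp findings at every visit, by arm and eye, with shift tables. These help with signs, but they do not capture symptoms or replace event counts by PT.

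**The tables are descriptive.** No test, significance level or success rule depends on them, and the patient-level half of the analysis is kept. This limits the importance of the point without removing the mismatch.

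**The requirement does not extend to every ocular table.** It would be easy to ask for event counts for the fellow eye and by severity as well. The protocol sets no event level for either, and a maximal-severity table holds one value per patient, so an event column does not fit it.

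**Conclusion.** The point holds within the following limits. The protocol's primary safety analysis requires study-eye ocular TEAEs by SOC and PT at patient and event level. SAP 15.1 provides the patient level only, and SAP section 17 does not declare the departure. Following the SAP as written would leave half of that named analysis undelivered, and the treatment-related version would have the same gap.

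The consequence is specific: repeat study-eye events of the same term would not be tabulated by term and arm. For m patients with k episodes each, the shortfall is m(k − 1) events for that term. It ranges from zero when nothing recurs to an amount that the documents give no basis for estimating. The efficacy analyses are not touched.

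The conclusion rests on reading the ocular sentence as it is written. It does not depend on whether the wording was deliberate or on any assumed repeat rate.

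**What to change.** Amend the ocular sentence in SAP 15.1 before unmasking, for example: *Study-eye ocular TEAEs will be summarized by SOC and PT for each treatment group as numbers of patients and numbers of events; fellow-eye ocular TEAEs will be summarized as numbers of patients.* State that the once-per-patient rule governs the patient counts only. Add an event-count column to the study-eye SOC/PT table and to its treatment-related version. Fellow-eye event counts are optional, and the maximal-severity table can stay at patient level.

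If the reduction is intended, leave SAP 15.1 as it is and record the change, with the reason, in SAP section 17.

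The cost is one reworded sentence, a short clarification and one extra column in two tables, or one entry in SAP section 17. The events are already recorded and listed individually, so nothing further has to be collected.

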15.2 Slit-Lamp Biomicroscopy

A slit-lamp biomicroscopy examination of the cornea, conjunctiva, anterior chamber, iris, lens, and lid will be performed for both eyes at each visit. The results will be graded as normal, abnormal not clinically significant (NCS) or abnormal clinically significant (CS).

The results will be summarized using counts and percentages for each treatment group and for all patients combined at each visit for each eye (study eye and non-study eye). Percentages will be based on the number of patients in each treatment group with responses. Shift tables for the slit-lamp biomicroscopy parameters will also be provided comparing each follow-up visit to baseline (Visit 2 [Day 1]). A patient listing of the slit-lamp biomicroscopy parameters will also be produced.

15.3 Dilated Indirect Ophthalmoscopic Examination

A dilated indirect ophthalmoscopic examination of the vitreous, retina, macula, choroid and optic nerve will be performed at Visit 1 (≥28 days prior to surgery) and Visit 6 (Day 21). The results will be graded as normal, abnormal NCS or abnormal CS.

The results will be summarized using counts and percentages for each treatment group and for all patients combined at each visit for each eye (study eye and non-study eye). Percentages will be based on the number of patients in each treatment group with responses. Shift tables for the dilated 13/FEB/2014

Confidential

Page 18 of 21

Statistical Analysis Plan Protocol RTA 408-C-1307

Version 1.0

indirect ophthalmoscopic examination parameters will also be provided comparing Visit 6 (Day 21) to baseline (Visit 1; ≥28 days prior to surgery). A patient listing of the dilated indirect ophthalmoscopic examination parameters will also be produced.

15.4 Pin-Hole Visual Acuity (ETDRS)

The logarithm of the minimum angle of resolution (logMAR) pin-hole visual acuity is assessed at each visit using an EDTRS chart. Pin-hole visual acuity should be done with a pin-hole occluder.

The observed and change from baseline pin-hole visual acuity will be summarized for each eye (study eye and non-study eye) using descriptive statistics (number of observations, mean, standard deviation (SD), median, minimum, and maximum values) by visit for each treatment group and for all patients combined. In addition, the proportion of patients with a worsening (increase) in their logMAR pin-hole visual acuity from the previous visit of ≥2 lines will be presented using frequency counts and percentages. A patient listing of pin-hole visual acuity will also be produced.

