	Visual Acuity data will be summarized at each visit, using discrete summaries including change from baseline in the number of lines and the proportion of patients with worsening from previous visit of ≥ 2 lines.
Summary of Known and Potential Risks and	This study is the first clinical study to evaluate the safety and efficacy of RTA 408 Ophthalmic Suspension.

Benefits to Human Patients	The ocular tolerability of RTA 408 was evaluated in multiple nonclinical studies in rats, guinea pigs, rabbits, and monkeys. No ocular or systemic toxicity was observed and systemic exposure was very low in all species tested. Conjunctival irritation was observed in the rabbit ocular GLP toxicity study with frequent dosing (4x/day); however, this was reversible, was not observed in a non-GLP study in rabbits, was not observed in the monkey ocular GLP toxicity study, and is readily monitorable in the clinic. In vitro and in vivo studies conducted to date demonstrate that RTA 408 is a potent activator of the Nrf2 pathway and an inhibitor of the NF- κ B pathway, and should thus be an effective anti-inflammatory agent for ophthalmic indications of inflammation and pain.
----------------------------	---

TABLE OF CONTENTS

SYN	OPSIS			3	
List o	of Abb	reviatio	ns	. 17	
1	INTRODUCTION				
2	STUDY OBJECTIVES				
3	CLIN	ICAL H	YPOTHESES	. 20	
4	OVEI	RALL S	ГUDY DESIGN	. 20	
5	STUDY POPULATION				
	5.1	Number	r of Patients	. 21	
	5.2	Study P	opulation Characteristics	. 21	
	5.3	Inclusio	n Criteria	. 21	
	5.4	Exclusio	on Criteria	. 22	
	5.5	Withdra	awal Criteria	. 24	
6	STUDY PARAMETERS				
	6.1	Efficacy	V Measures	. 24	
		6.1.1	Secondary Efficacy Variables	. 24	
	6.2	Safety N	Aeasures	. 24	
	6.3	Other N	Ieasures	. 25	
7	STUD	Y MAT	ERIALS	. 25	
	7.1	Study T	reatments	. 25	
		7.1.1	Study Treatments/Formulations	. 25	
		7.1.2	Instructions for Use and Administration	. 25	
	7.2	Other S	tudy Supplies	. 25	
8	STUD	Y MET	HODS AND PROCEDURES	. 26	
	8.1	Patient	Entry Procedures	. 26	
		8.1.1	Overview	. 26	
		8.1.2	Informed Consent	. 26	
		8.1.3	Washout Intervals	. 26	
		8.1.4	Procedures for Final Study Entry		
		8.1.5	Methods for Assignment to Treatment Groups		
	8.2	Concur	rent Therapies		
		8.2.1	Prohibited Medications/Treatments		
		8.2.2	Escape Medications	. 28	
	0.0	8.2.3	Special Diet or Activities	. 29	
	8.3	Examin	ation Procedures	. 29	
		8.3.1	Procedures to be Performed at Each Study Visit with Regard	•	
	0.4	to Study		. 29	

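### SAP 15.4 drops the protocol's lines-from-baseline acuity summary without declaring it, so eyes with a cumulative loss of 2 or more lines are not counted by arm

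*SAP*

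**What the plan says.** Protocol Section 10.12 asks for discrete acuity summaries at each visit, "including change from baseline in the number of lines and the proportion of patients with change from previous visit of ≥ 2 lines". The synopsis plans the same pair of outputs, with one word different: "including change from baseline in the number of lines and the proportion of patients with worsening from previous visit of ≥ 2 lines".

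SAP 15.4 handles the two parts differently.

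- **Change from baseline** becomes a continuous summary: "The observed and change from baseline pin-hole visual acuity will be summarized for each eye (study eye and non-study eye) using descriptive statistics". The statistics are the number of observations, mean, "standard deviation (SD), median, minimum, and maximum values) by visit for each treatment group and for all patients combined".
- **The threshold** stays categorical and stays tied to the preceding visit: "worsening (increase) in their logMAR pin-hole visual acuity from the previous visit of ≥2 lines".
- **Patient-level data:** "A patient listing of pin-hole visual acuity will also be produced".

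SAP Section 6 sets the acuity baseline at Visit 2 (Day 1, the day after surgery). SAP Section 17 reports one departure from the protocol, the imputation for the Per Protocol population. It says nothing about acuity.

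**The concern.** The protocol paired two acuity summaries that cover for each other. A count of 2-line losses between consecutive visits picks up sudden drops. A distribution of lines gained or lost since baseline picks up cumulative change. The SAP keeps the first and turns the second into continuous statistics, so no categorical comparison of acuity with baseline remains.

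This is out of step with the SAP's other eye examinations. Intraocular pressure has a count of rises of at least 10 mm Hg from baseline (SAP 15.5). Slit-lamp and dilated ophthalmoscopic findings have shift tables against baseline (SAP 15.2 and 15.3).

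Loss of vision is a harm to individual patients, and the natural safety question is how many eyes in each arm ended materially worse than they started. Safety is part of the primary objective, acuity is a named safety measure, and the synopsis describes this as the first clinical study of the suspension. A promised safety output should not disappear without being declared.

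**Working it through.** **Inputs**

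- Scoring: 0.02 logMAR per letter missed, 5 letters per line (Protocol Appendix 1, logMAR calculation).
- Baseline: Visit 2 (SAP Section 6).
- Post-baseline visits: 3, 4, 5 and 6, so four visit-to-visit steps.
- Arm size: 35 enrolled, 31 planned completers (Protocol 5.1).

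**1. The protocol's own scoring example.** The patient reads 4 of 5 letters on the 0.2 line and 2 of 5 on the 0.1 line. N = (5 − 4) + (5 − 2) = 4, and logMAR = 0.1 + 4 × 0.02 = 0.18. This matches the protocol's figure.

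**2. The threshold in logMAR.** One line = 5 × 0.02 = 0.10. Two lines = 0.20.

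**3. A steady loss of 1 line per step**

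| Visit | Change from previous visit | Counted by SAP threshold | Change from Visit 2 | At least 0.20 from Visit 2 |
|---|---|---|---|---|
| 3 | 0.10 | no | 0.10 | no |
| 4 | 0.10 | no | 0.20 | yes |
| 5 | 0.10 | no | 0.30 | yes |
| 6 | 0.10 | no | 0.40 | yes |

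The total loss is 4 × 0.10 = 0.40 logMAR, or 4 lines. The SAP threshold counts it zero times. A threshold against baseline would count it from Visit 4 onward.

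**4. The largest steady loss that escapes.** Nine letters per step is 9 × 0.02 = 0.18, which is below 0.20. Ten letters is 0.20 and is counted. Four steps of 0.18 give 0.72 logMAR, which is 36 letters or 7.2 lines. This is a bound, not a forecast.

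**5. What the continuous summary shows of one such eye**

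| Loss in one eye | Shift in arm mean, n = 35 | Shift in arm mean, n = 31 |
|---|---|---|
| 0.40 | 0.40/35 = 0.011 | 0.40/31 = 0.013 |
| 0.72 | 0.72/35 = 0.021 | 0.72/31 = 0.023 |

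The mean barely moves. The maximum does respond: with the 0.40 eye in the arm, the Visit 6 maximum change is at least +0.40. But a maximum is one eye's value. It would be the same whether one eye or five had lost that much.

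**6. The reverse case (assumed values, since the documents give no acuity data).** An eye measures 0.50 at Visit 2, 0.10 at Visit 4 and 0.40 at Visit 5. From Visit 4 to Visit 5 it loses 0.30 (3 lines), and the previous-visit threshold counts it. Against Visit 2 the change is 0.40 − 0.50 = −0.10, so a baseline threshold misses it. Neither reference covers both patterns.

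**The case against.** The strongest reply is that cumulative loss is not hidden. SAP 15.4 reports the median, minimum and maximum change from baseline by visit and arm, and lists every patient's values. Ocular treatment-emergent adverse events are tabulated by arm for study and fellow eyes separately (SAP 15.1). This stands. A reader might infer that a steady loss is never visible, or that change from baseline is reduced to a group mean. The documents support neither. It does not close the gap, though. A maximum and a listing give no count or proportion by arm, and the adverse event tables hold only losses reported as events.

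A second reply is that the previous-visit reference is the protocol's own and has merit, because the baseline is the day after surgery and eyes may recover before they lose. This also stands, as step 6 shows. It is a reason to keep that count, not to leave out the other. The SAP's departure is in dropping the companion summary.

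Third, a count at any post-dose visit will include dips that later recover. That is true. The by-visit counts, read at Visit 6, separate lasting losses from passing ones.

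Finally, a reader might infer from the word change in Protocol 10.12 that 2-line gains would be counted as safety events. The synopsis and the SAP both say worsening, so under the SAP as written they would not be. Only a clerical mismatch remains.

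**Conclusion.** The point holds in a limited form. The SAP replaces a discrete lines-from-baseline summary, planned in two places in the protocol, with continuous statistics and does not declare it. The only categorical acuity threshold left cannot count a gradual loss: 4 lines in the 1-line-per-step example, and up to 7.2 lines at the bound. The number of eyes per arm with a cumulative loss of at least 2 lines is therefore not tabulated.

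The loss figures assume an even decline over the four steps from Visit 2. The documents give no acuity data, so nothing here says how often that would occur. The undeclared departure rests on no such assumption.

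The safety analyses are descriptive and no success criterion depends on acuity. This should be corrected, but it does not threaten the trial's primary conclusions.

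**What to change.** In SAP 15.4 and Table 14.3.2.3:

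- Restore the distribution of change from baseline in lines, by visit and arm.
- Add, by arm, n (%) of study eyes with worsening of at least 2 lines (at least 0.20 logMAR) from baseline, at each visit and at any post-dose visit.
- Keep the previous-visit count, because a Day 1 post-operative baseline can miss a loss that follows recovery.
- State in the table that baseline is Visit 2.

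If the sponsor prefers not to restore the protocol's summary, the minimum is to declare the change in SAP Section 17. Separately, as a clerical correction, bring the wording of Protocol 10.12 into line with the synopsis.

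The cost is a few more rows in a planned table. Acuity is already measured at every visit, so no new data are needed.
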